### **8.9.3 Exploratory Analyses**

#### Clinician Administered PTSD Scale-4 (CAPS-4)

- The percentage of subjects who achieve a 30% drop in CAPS-4 global score at the primary endpoint will be an indirect measure of clinical significance. Descriptive statistics will be computed and displayed by Stage 1 conditions.
- The percentage of subjects who no longer meet PTSD diagnostic criteria at the primary endpoint will be an indirect measure of clinical significance. Descriptive statistics will be computed and displayed by Stage 1 conditions.
- CAPS-4 Subscale Scores (B, C, D, F) at the primary endpoint will be analyzed in the same manner as the primary analysis of the global score. Descriptive statistics will be computed and displayed by Stage 1 conditions.
- Distributional characteristics will be examined for outliers and extreme values and, if either is evident. If outliers are found in primary or secondary outcome measures, the sponsor will perform analyses with and without the outlying data

### **8.9.3.1 Process Measures**

#### States of Consciousness Questionnaire (SOCQ)

Descriptive statistics will be computed for SOCQ scores completed after each MDMA-assisted psychotherapy session, and SOCQ scores will be compared by initial dose using ANOVA for overall differences and t-tests for pairwise comparisons for each experimental session. The data will be explored for effects of dose on composite and total SOCQ scores.

#### Long-term Follow-up Questionnaire (LTFU Questionnaire)

The LTFU Questionnaire nominal variables will be described in terms of frequencies and percentages, while ordinal and non-normal continuous variables will be described using sample mean, standard deviations, and range.

#### Belief of Condition Assignment

In order to compare the therapists', independent raters', and subjects' belief of condition to actual MDMA dose received in each blinded session, the frequency of correct guesses will be calculated and depicted by dose condition and study role (subject, therapist, or independent rater).

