MAPS' initial U.S. pilot study enrolled 21 subjects, a majority (17) of whom were women suffering from PTSD related to sexual assault and/or childhood sexual abuse[1, 2]. Only two subjects had PTSD from war-related trauma (U.S. veterans of the Iraq War) and both were male. According to the European Medicines Agency (EMEA) Guideline for the Development of Medicinal Products for the Treatment of PTSD, it is desirable to examine treatment response in homogenous samples, conducting separate trials for different populations. The findings from this proposed study in veterans, firefighters and police officers with service related trauma will be compared with results from our initial U.S. pilot study, mostly in women survivors of sexual abuse and assault.

In order to refine our triple-blind methodology, the proposed study will also evaluate three different doses of MDMA to determine their relative success in achieving blinding of therapists, subjects, and independent raters.

In addition, this will be the first study of MDMA-assisted psychotherapy to permit the enrollment of subjects with two medical conditions that were exclusion criteria in the previous trial; Hepatitis-C, and controlled hypertension. Should any subjects with these conditions seek enrollment in the study, they will be required to go through additional specified screening procedures and additional monitoring for safety during the experimental sessions.

A review of the published, peer-reviewed MDMA research literature is contained in the Investigator's Brochure supplied by the sponsor. This document should be reviewed by the investigator prior to initiating the protocol.

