#### **6.1.3 Process Measures**

Adherence criteria and competence ratings will be conducted by qualified, trained blinded adherence raters who will analyze audio/video data from selected preparatory, experimental and integrative sessions. Participants will be asked to read a brief script for a computer program that will enable transcription of audio recordings from these sessions. The elements included in adherence criteria are specific to each type of session. The goal of these ratings will be to correlate therapist adherence to the Treatment Manual with outcome as a part of the sponsor's ongoing efforts to standardize treatment methods of MDMA-assisted psychotherapy for PTSD.

Belief of condition assignment and certainty will be collected from each therapist responsible for treating the subject and the subject at the integrative session on the day after each blinded experimental session in Stage 1. At the primary endpoint, the Independent Rater for the study will also provide their guess and certainty of condition

assignment prior to unblinding. These beliefs are collected as a part of the sponsor's ongoing initiative to optimize the triple-blind as a part of dose response studies.

Subject opinions about having three versus two experimental sessions will be collected from each subject at the Primary Endpoint after unblinding and the 2-month follow-up in Stage 1. Stage 2 subjects will complete the same measure at the Secondary Endpoint and the 2-month follow-up in Stage 2. These opinions (referred to as "perceptions" in the Time and Events Table) are collected as a part of the sponsor's ongoing initiative to assess the therapeutic value of the third experimental session and to gather information on the optimal therapeutic dose for MDMA.

The Reactions to Research Participation Questionnaire (RRPQ) [98] is an assessment of causes for taking part in research and responses to the experience of being a research subject. Subjects will complete this measure during their 2-month follow-up, with exact time of completion varying in accordance with participation in the third open label experimental session in Stage 1 or in Stage 2. The RRPQ is intended to assess the subject's experience as a research subject, perceived reasons for consenting to be a research subject and perceived freedom to take part in the study.

Table 3.Stage 1 Time&Events	Screen/Baselin	Preparatory	Experimenta	al Session 1	Expe	rimental Sess	sion 2	Experimenta	Follow-Up			

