MAPS’ initial U.S. pilot study, conducted at the same site as this study, enrolled 23 subjects, of which 20 were evaluable, with a majority of whom were women suffering from PTSD related to sexual assault and/or childhood sexual abuse (N=18) [1, 2]. Only two subjects had PTSD from war-related trauma (U.S. veterans of the Iraq War) and both were male. According to the European Medicines Agency (EMA) Guideline for the Development of Medicinal Products for the Treatment of PTSD, it is desirable to examine treatment response in homogenous samples, conducting separate trials for different populations. The findings from this study in veterans, firefighters and police officers with service related trauma will be compared with results from our initial U.S. pilot study, mostly in women survivors of sexual abuse and assault.

In order to refine our triple-blind methodology, MP-8 will evaluate three different doses of MDMA to determine their relative success in achieving blinding of therapists, subjects, and independent raters.

In addition, this will be the first study of MDMA-assisted psychotherapy to permit the enrollment of subjects with two medical conditions that were exclusion criteria in the previous trial: Hepatitis-C, and controlled hypertension. Should any subjects with these conditions seek enrollment in the study, they will be required to go through additional specified screening procedures and additional monitoring for safety during the experimental sessions.

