#### 3.2 Secondary Objectives

The following objectives will compare full, medium and low dose subjects in the blinded portion of Stage 1:

- Assess changes in posttraumatic growth via Post Traumatic Growth Inventory (PTGI) scores from baseline to the primary endpoint.
- Assess changes in global functioning via Global Assessment of Functioning (GAF) scores from baseline to the primary endpoint.
- Assess changes in symptoms of depression via Beck Depression Inventory-II (BDI-II) scores from baseline to the primary endpoint.
- Assess changes in self-reported sleep quality via the Pittsburgh Sleep Quality Index (PSQI) from baseline to the primary endpoint.
- Assess self-reported dissociation symptoms with the Dissociative Experiences Scale-II (DES-II) from baseline to the primary endpoint.
- Assess changes in Neuroticism-Extroversion-Openness Personality Inventory (NEO PI) scores from baseline to the primary endpoint.

The following objectives will include exploratory analyses intended to inform protocol design:

- Explore the effects of each MDMA-assisted psychotherapy session upon self-reported changes in consciousness, as those associated with a transformational or mystical experience via the States of Consciousness Questionnaire (SOCQ).
- Assess the effects of a third active dose experimental session by comparing Global CAPS, BDI-II, GAF, PSQI, PTGI (in reference to start of the study), and DES-II scores at the primary/secondary endpoint and end of Stage 1/ Stage 2 in subjects receiving a third experimental session in Stage 1 and Stage 2.
- Assess the ability of the investigators and subjects to accurately guess condition assignment when asked to do so after each blinded experimental session.
- Assess value of third experimental session in Stage 1/Stage 2 by collecting each active dose subject's perception of experimental sessions at the primary/secondary endpoint and end of Stage 1/ Stage 2.
- Correlate adherence to the Treatment Manual with Global CAPS scores using adherence criteria ratings to assess videos of psychotherapy sessions.
- Assess PTSD symptoms via CAPS, posttraumatic growth via PTGI, depression symptoms via BDI-II, global functioning via GAF, sleep quality via PSQI, dissociation symptoms via DES-II, and personality via NEO PI throughout Stage 2 in comparison to Stage 1 in crossover subjects.

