## **5.0 Randomization and Blinding**

This is a randomized, triple-blind, dose response study with an open-label cross-over segment. For Stage 1, a randomization list will be prepared at the beginning of the study. If needed, subsequent randomization lists will be created to replace subjects who withdraw from the study to ensure that replacement subjects are not added to the end of the initial list. Each subject will be assigned to one of the three dose conditions; 30 mg (low dose), 75 mg (medium dose) or 125 mg (full dose). Twelve evaluable subjects will be assigned to the full dose condition, six evaluable subjects to the 75 mg condition and six evaluable subjects to the 30 mg low dose condition. The study will employ a blinded randomization procedure that will maintain the 2:1:1 ratio while maintaining the blind and ensuring that each subsequent condition assignment is not predicated on the previous assignment.

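### The blinding analysis counts only correct guesses per dose, which hides the dose named in wrong guesses and the certainty ratings, so an arm's rate mixes dose recognition with answer preference

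*SAP*

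**What the plan says.** Both documents make blinding a question of the trial. Protocol 2.1 says the three doses are evaluated to "determine their relative success in achieving blinding of therapists, subjects, and independent raters", and SAP 2.0 repeats it. SAP 3.2 lists a matching objective among the exploratory analyses meant to inform protocol design: "Assess the ability of the investigators and subjects to accurately guess condition assignment".

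The data are richer than the analysis. Under Protocol 6.1.3, "Belief of condition assignment and certainty will be collected from each therapist responsible for treating the subject and the subject", on the day after each blinded session. The independent rater gives a guess and a certainty at the primary endpoint, before unblinding.

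The only analysis specific to these data is in SAP 8.9.3.1: "the frequency of correct guesses will be calculated and depicted by dose condition and study role". It gives no chance benchmark, no interval, no tabulation of wrong guesses and no use of certainty. Protocol 12.0 contains no analysis of beliefs.

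SAP 8.0 adds two general rules. Nominal variables are described by frequencies and percentages and analysed by chi-square. Data that the plan does not analyse go into the listings and not into tables or graphs.

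**The concern.** With three possible answers, a wrong guess is informative. A low-dose subject who says medium has told us something different from one who says full. Counting only correct guesses discards that difference.

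What remains in each arm is the chance of naming that arm's dose. It rises if people recognise the dose, and it also rises if people simply favour that answer. A high rate in the full-dose arm can mean that 125 mg is easy to recognise, or that most people say full whatever they received. The stated aim is to compare doses, and a side-by-side reading of three such rates invites the conclusion that one dose is unblinded and the others are well blinded. Answer preference alone can produce that picture. At stake is what the sponsor learns about the choice of comparator dose for later trials.

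**Working it through.** The plan states no expected guess rate, threshold or power for blinding, so there is no figure of its own to reproduce. The guess patterns below are assumptions chosen to test the display; the documents give no guess data.

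**Inputs.** Arm sizes of 12 full, 6 medium and 6 low, total 24 (SAP 5.0 and Table 4.0-1). Three possible answers: full (F), medium (M), low (L).

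**Step 1: three patterns, one display.** Cells give the number answering F/M/L.

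| Pattern | Full arm (12) | Medium arm (6) | Low arm (6) | Correct, by dose |
|---|---|---|---|---|
| A: always names full | 12/0/0 | 6/0/0 | 6/0/0 | 12/12, 0/6, 0/6 |
| B: recognises full, swaps medium and low | 12/0/0 | 0/0/6 | 0/6/0 | 12/12, 0/6, 0/6 |
| C: calls medium full and low medium | 12/0/0 | 6/0/0 | 0/6/0 | 12/12, 0/6, 0/6 |

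In A the answer does not depend on dose. In B it identifies the dose exactly, though with two labels exchanged. In C it separates low from the rest. The planned display is identical for all three.

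**Step 2: what the full table adds.** P(names full | full) is 12/12 in every pattern. P(names full | not full) is 12/12 in A, 0/12 in B and 6/12 in C.

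For the whole table, X² = N(Σ nᵢⱼ²/(rᵢcⱼ) − 1), with row totals r and column totals c:
- A: 24 × (144/288 + 36/144 + 36/144 − 1) = 24 × (1 − 1) = 0
- B: 24 × (144/144 + 36/36 + 36/36 − 1) = 24 × 2 = 48
- C: 24 × (144/216 + 36/108 + 36/36 − 1) = 24 × 1 = 24

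**Step 3: the general chi-square rule applied to correct versus incorrect.** Overall 12 of 24 are correct, so the expected counts are 6 and 6 in the full arm and 3 and 3 in each lower arm. The observed counts are 12 and 0, 0 and 6, 0 and 6. X² = 2 × 6²/6 + 4 × 3²/3 = 12 + 12 = 24 on 2 df, p = exp(−12), about 0.000006. Pattern A, with no information, gets this result.

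**Step 4: how far the split by dose helps.** If guesses ignore dose, with probabilities q for each answer, the correct rate in an arm is the q for that arm's dose. The three rates then sum to 1. Perfect unblinding gives 100/100/100%, sum 3. Half correct in every arm gives 50/50/50%, sum 1.5, with standard error √(0.25/12 + 0.25/6 + 0.25/6) = 0.32. A sum well above 1 shows real information, but a sum of 1 does not show its absence: B and C also sum to 1.

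**Step 5: precision.** Exact (Clopper-Pearson) 95% intervals: 0/6 is 0–46%, 3/6 is 12–88%, 6/6 is 54–100%, 12/12 is 74–100%. A permutation test of the 3×3 table at 0.05 (400 simulated trials, 300 permutations each) rejected in 4.5% of trials when guesses were made in fixed 2:1:1 proportions regardless of dose. It rejected in 22% when half were correct in every arm, 87% when 70% were correct in every arm, and 100% for patterns B and C. In the 50% and 70% scenarios wrong guesses were split equally between the other two doses.

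**The case against.** The strongest reply is that the SAP splits correct guesses by dose. A reader might infer from the above that the display cannot tell real unblinding from a habit of naming full dose. That is not supported: the habit shows as 100/0/0% and full unblinding as 100/100/100%.

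A reader might also blame the 2:1:1 allocation, since someone who always names full is right for 12 of 24 subjects. That concerns accuracy pooled over arms, which the SAP does not plan. The chance of a correct answer within an arm does not depend on arm sizes.

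Other points also have weight. SAP 8.0 has a chi-square rule for nominal variables, but the belief section does not apply it to guesses. Applied to the 3×3 table it would be useful; applied to correct versus incorrect it misleads, as Step 3 shows. Guesses and certainty are not lost, since they remain in the listings and labelled post-hoc analyses are allowed. But a stated question should not depend on either. The objective is exploratory, no efficacy or safety analysis in the SAP depends on it, and six subjects per lower arm allow little precision whatever is reported.

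What stands is that the display collapses patterns A, B and C, and that certainty has no planned use.

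**Conclusion.** The point holds as a gap in the analysis of an exploratory aim. Correct-guess rates by dose distinguish the extremes, but they do not show whether an arm's rate reflects recognition or preference. They give the same 12/12, 0/6, 0/6 for one uninformative pattern and two informative ones.

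It would go too far to infer that the plan will give a wrong answer on blinding. The SAP sets no threshold or decision rule for blinding, and a descriptive display can be incomplete without being wrong. The primary CAPS-4 comparison is not affected.

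The conclusion rests on 12, 6 and 6 evaluable subjects and one guess per subject per table. Patterns A to C are constructed and extreme; real guesses will be mixed, and their ambiguity less complete. The full table removes the ambiguity but not the imprecision: with half of guesses correct in every arm, a test of the table would detect dose dependence only about 22% of the time.

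**What to change.** In SAP 8.9.3.1, replace the correct-guess frequencies with the following.

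- For each role and each blinded assessment, give the 3×3 table of guessed by assigned dose, with exact 95% intervals for the proportions in each row. Tabulate the two therapists separately, so that each table has one guess per subject. The rater has one table, at the primary endpoint.
- Summarise certainty within the cells of the table, for example by median and range, in line with the SAP 8.0 rule for ordinal variables.
- Base any statement on relative blinding success on whether the distribution of guesses differs by assigned dose. Suitable forms are P(names full | full) against P(names full | not full), or an exact or permutation test of the 3×3 table.

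Kappa or per-arm blinding indices may be added but should not be used to rank doses. A per-arm index built on correct guesses rescales that arm's percent correct, so always naming full puts it at its maximum in the full arm and its minimum in the others. Kappa is one number for all doses. It is 0 for pattern A, but only (0.5 − 0.375)/(1 − 0.375) = 0.20 for B and (0.5 − 0.4375)/(1 − 0.4375) = 0.11 for C.

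The cost is one table shell and a few sentences. No new data are needed and trial conduct does not change: a free improvement.

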#### Subject's Perceptions of Experimental Sessions

Descriptive statistics will be calculated for subject's perceptions of experimental sessions. Mean, standard deviation and range of individual responses and sum of items #1-4 will be examined. For the 125 mg group, within-subjects t-tests will be performed on subject's perceptions at Stage 1 primary and secondary endpoints. The same analysis will be performed for 30 mg and 75 mg groups, but data will be from Stage 2 primary and secondary endpoint.

#### Reactions to Research Participation Questionnaire (RRPQ)

Frequency of response will be tabulated for 'reasons for participation' across Stage 1 conditions. Descriptive statistics will be computed for total scores for subscales and displayed by Stage 1 conditions.

#### Adherence to the Treatment Manual

The sponsor will collect ratings of adherence to the treatment manual from specifically selected types of sessions. Descriptive statistics will be computed for each adherence scale within a given session. If sufficient data is available, the sponsor will correlate the mean adherence ratings for adherence scale and session type with Global CAPS scores from the closest available endpoint assessment to investigate the effects of adherence to the treatment manual on reduction in PTSD symptoms.

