The sponsor will collect ratings of adherence to the treatment manual from specifically selected types of sessions. Descriptive statistics will be computed for each adherence scale within a given session. The sponsor will explore the factors and structure of the measures of adherence to assist in further development of adherence and competence measures. If sufficient data is available, the sponsor will correlate the mean adherence ratings for adherence scale and session type with Global CAPS scores to investigate the effects of adherence to the treatment manual on reduction in PTSD symptoms. If it is found that there are specific factors within the adherence scales, then the factor will be correlated with Global CAPS score.

Qualitative interviews conducted by a researcher who is part of the study team during the 12-month follow-up visit will be transcribed to text. A computer-assisted qualitative data analysis software package will be utilized to assist in thematic content analysis of the interview transcripts. A member of the research team will code the interviews for content, to identify emerging themes and organize data into thematic constructs utilizing a grounded theory approach. Descriptive statistics will be calculated for emerging themes.

There may be an interim analysis of the data that will not affect study conduct for safety and efficacy before all participants have completed the 12-month follow-up.

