## 1.0 List of Abbreviations and Definitions of Terms

### Definitions of Terms

*Categorical data:* refers to discrete (indivisible) variables, such as gender or ethnicity; data will be presented as total numbers of each category as needed to describe the sample

*Descriptive data:* includes mean, median, standard deviation, minimum and maximum of numerical data used as needed to describe the sample

*Difference scores:* consist of scores computed by subtracting one value from another, as subtracting baseline from End of Stage 1 score, used to test for differences between and within groups to determine change as a function of experimental treatment over time

*Efficacy:* type of analysis used to assess therapeutic effects or benefits

*Exploratory analyses:* inferential or descriptive analysis of the data to determine trends that might lead to hypotheses for further study

*Frequency listing:* tabular listing of numbers and/or percentages of events used as needed to describe the sample or data characteristics

*Outcome measures:* primary and secondary study measures that are used to test the study hypotheses

*Process measures:* study measures or qualitative observations collected during the study that may increase depth of understanding and that are not necessarily related to safety or efficacy

*Protocol deviation:* event that represents significant divergence from the intended study design as described in the protocol

*Safety:* assessment of the condition of study subjects that examines potential risks, adverse events, and reactions

*Safety measures:* study measures that assess safety, such as heart rate monitoring, that are used to assess safety of the study drug

*Spontaneously reported reactions, reactions:* specific expected reactions gathered from the literature on MDMA

*Study design:* all elements of a research project that define the study question, experimental methods, study procedures including blinding and randomization, measurement techniques, flow sheet of data, and statistical analysis

*Tabular listing:* list of each variable or item for each individual subject either in total or by condition in a table format

List of Abbreviations

|        |   |
|--------|---|
| AE     | Adverse Event   |
| ANOVA  | Analysis of Variance                                    |
| BDI-II | Beck Depression Inventory-II                            |
| BT     | Body Temperature  |
| CAPS-4 | Clinician Administered PTSD Scale-4                     |

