| Visit Timing or Study day or Window        | Up to 2 months prior to Visit 1                 |            | Prior to V5 M | Up to 7 weeks post V1  | Before V9 A | 3-5 weeks post V5      | Before V13 A | 1 month post V9  | 3-5 weeks post V9 N | Before V18 A, N | May happen over > 1 day. 2 mo. post V14 N |
| Initial Phone Screen                       | X   |            |                          |                        |                        |                        |                         |                  |                                |                            |  |
| Informed Consent                           | X   |            |                          |                        |                        |                        |                         |                  |                                |                            |  |
| Medical/Psychiatric History                | X   |            |                          |                        |                        |                        |                         |                  |                                |                            |  |
| General Phys. Exam (BP, Heart rate, Temp)  | X   |            |                          |                        |                        |                        |                         |                  |                                |                            |  |
| Brief Neurological Exam                    | X   |            |                          |                        |                        |                        |                         |                  |                                |                            |  |
| ECG  | X   |            |                          |                        |                        |                        |                         |                  |                                |                            |  |
| SCID-I-RV                                  | X   |            |                          |                        |                        |                        |                         |                  |                                |                            |  |

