| Visit #                                    | Preparatory Session                | Experimental Session 1 | Integrative Sessions    | Experimental Session 2 | Integrative Sessions    | Secondary endpoint           | Experimental Session 3 | Integrative Sessions    | End of Stage 2 & Outcome                  | 1 Year Follow-up                                  |
| Type of Visit                              | Within maximum of 5 months of V13* | After V19              | Before V24 A | 3-5 weeks post V20     | Before V28 A | 1 month post V24, before V29 | 3-5 weeks post V24     | Before V33 A | May happen over > 1 day 2 months post V29 | Follow-Up & Outcome                               |
| Visit Timing or Study day or Window        |                                    |                        |                         |                        |                         |                              |                        |                         |   | May happen over > 1 day. One Year post V14 or V29 |
| Confirm Informed Consent                   | X                                  |                        |                         |                        |                         |                              |                        |                         |   |   |
| Confirm Inclusion/Exclusion                | X                                  |                        |                         |                        |                         |                              |                        |                         |   |   |
| Enrollment in Stage 2                      | X                                  |                        |                         |                        |                         |                              |                        |                         |   |   |
| Collect Concomitant Medication             | X                                  | X                      | X                       | X                      | X                       | X                            | X                      | X                       | X   | X   |
| Record to Audio/Video                      | X                                  | X                      | X                       | X                      | X                       | X H               | X                      | X                       | X H                            |   |

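### The adherence analysis uses a raw CAPS score where the aim is symptom reduction, and linking to the nearest visit would pair third-session ratings with a CAPS taken before the session

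*SAP*

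**What the plan says.** SAP 3.2 lists this among the exploratory objectives: "Correlate adherence to the Treatment Manual with Global CAPS scores using adherence criteria ratings to assess videos of psychotherapy sessions". SAP 8.9.3.1 (Adherence to the Treatment Manual) gives the method. If the data suffice, the sponsor will "correlate the mean adherence ratings for adherence scale and session type with Global CAPS scores from the closest available endpoint assessment", and the purpose is "to investigate the effects of adherence to the treatment manual on reduction in PTSD symptoms". The section does not define *closest*, takes no difference score and adjusts for no earlier CAPS. The SAP does have the tool: its definitions of terms say that difference scores "consist of scores computed by subtracting one value from another", and the primary CAPS analysis in 8.9.1 uses one.

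Protocol 12.0 plans to "correlate the mean adherence ratings for adherence scale and session type with Global CAPS scores to investigate the effects of adherence". It names no CAPS visit, and it adds a further step: "If it is found that there are specific factors within the adherence scales, then the factor will be correlated with Global CAPS score". Protocol 6.1.3 says that only a selection of sessions, of the preparatory, experimental and integrative types, will be rated, and that the goal is to relate adherence to outcome.

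The visit timing is in the two parts of SAP Table 4.1:
- **Stage 1:** V13 is one month after V9, V14 is three to five weeks after V9, and the entry for V18 reads "May happen over > 1 day. 2 mo. post V14".
- **Stage 2:** the entry for V28 reads "1 month post V24, before V29", V29 is three to five weeks after V24, and V33 is two months after V29.

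**The concern.** There are two separate problems.

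**Quantity.** The question is about reduction, but the variable is a level at one visit. A subject who starts very ill and improves greatly can still end with a high score. If adherence ratings are related to how ill the subject was at the start, for whatever reason, a raw-score correlation picks that up.

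**Order in time.** The third session comes shortly after one CAPS and about two months before the next. A programmer who takes *closest* as nearest in time would attach third-session ratings to a CAPS already completed when the session took place. A correlation of that kind might reflect prior severity or the effect of earlier sessions, but not the session that was rated.

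The result is meant to inform the sponsor's standardisation of the treatment (Protocol 6.1.3), so a correlation that runs the wrong way in time, or carries baseline severity, could be misread as evidence about the manual. No primary, secondary or safety result depends on it.

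**Working it through.** The plan gives no sample size, power or expected correlation for this analysis, so there is no figure to reproduce.

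**1. Which CAPS is nearest to a third session?** Take one month as 365.25/12 = 30.44 days.
- V13 is at day 30.4 after V9, and V14 is at day 35 at the latest. Protocol 5.0 places the full-dose third session after unblinding, and Protocol 6.2.7 has its scheduling discussed at V13, after the rater's CAPS. V14 therefore follows V13 by about 0 to 35 − 30.4 = 4.6 days.
- V18 is 2 × 30.44 = 60.9 days after V14, so V13 is the nearer CAPS. This does not depend on exact windows: V13 stays nearer unless V14 slips more than 60.9 days past it.
- An integrative session *d* days after V14, with V14 *g* days after V13, is nearer V13 when g + d < 60.9 − d, that is, d < (60.9 − g)/2. For g = 0 to 4.6 the limit is 30.4 to 28.2 days. Protocol 6.2.6 puts the remaining integrative sessions in the month after the last experimental session, so most fall inside the limit.
- In Stage 2, V28 is explicitly before V29 and V33 is 60.9 days after V29, which gives the same result.
- V28 is (21 to 35) + 30.4 = 51.4 to 65.4 days after V20. If V20 comes sooner than that after V13, its nearest endpoint CAPS is V13, which reflects the low or medium dose.

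**2. Which pairings are in the right order?** V13 is 51.4 to 65.4 days after session 1 (V5) and 30.4 days after session 2 (V9). Stage 1 preparatory sessions come before both. The screening CAPS is a baseline, not an endpoint, so all of these link forward to V13.

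**3. Raw score, change or adjusted score?** Let *r* be the pre-post CAPS correlation, with equal SDs, and *g* now the correlation of adherence with the starting score. Neither is in the documents; r = 0.3 to 0.7 and g = 0.2 to 0.4 are assumptions.

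If g = 0 and the correlation with change is ρ, the raw-score correlation is ρ√(2(1 − r)): 1.18ρ, 1.00ρ and 0.775ρ for r = 0.3, 0.5 and 0.7. The raw score is then informative.

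If adherence has no effect but g is not zero:

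| g | r | Raw score: g·r | Change: −g√((1 − r)/2) |
|---|---|---|---|
| 0.2 | 0.3 | 0.06 | −0.118 |
| 0.2 | 0.5 | 0.10 | −0.100 |
| 0.2 | 0.7 | 0.14 | −0.077 |
| 0.4 | 0.3 | 0.12 | −0.237 |
| 0.4 | 0.5 | 0.20 | −0.200 |
| 0.4 | 0.7 | 0.28 | −0.155 |

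The numerator of the partial correlation given the starting score is g·r − g·r = 0. Only the adjusted analysis is free of the distortion in this model.

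**4. What does the pre-session pairing cost?** Simulation with 20,000 runs, two-sided α = 0.05, assumed r = 0.5, third-session adherence independent of the V13 score, and a true correlation of 0.5. The table gives rejection rates. There are 12 full-dose subjects with a Stage 1 third session; 24 adds up to 12 from Stage 2.

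| n | Paired with V13 | Raw V18 | Change V13 to V18 | Partial, given V13 |
|---|---|---|---|---|
| 12 | 0.051 | 0.397 | 0.396 | 0.491 |
| 24 | 0.049 | 0.726 | 0.727 | 0.849 |

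Paired with V13, the test rejects at its nominal error rate and no more.

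**5. Precision after correction.** The smallest correlation detectable with 80% power is tanh((1.960 + 0.842)/√(n − 3)): 0.73 at n = 12 and 0.55 at n = 24.

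**The case against.** The strongest reply is that this is a loosely worded exploratory analysis, not a demonstrated error. Four parts of that reply stand.

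- **Scope.** A reader might infer that the analysis as a whole cannot show an effect of adherence. The schedule does not support that. The CAPS follows Stage 1 preparatory sessions and sessions 1 and 2, and a post-treatment score can carry an effect (step 3).
- **Reading of the rule.** *Closest* is undefined and might have been meant as the next assessment, which suits the stated purpose better. The backward pairing follows from the plain reading; it is not an explicit instruction. Protocol 12.0 names no CAPS visit, so the timing problem is in the SAP only.
- **Sessions affected.** A reader might also infer that a third-session correlation is spoiled for every full-dose subject and every Stage 2 completer. Only selected sessions are rated, and ratings are averaged by session type, so a separate third-session correlation is not certain. Averaging does not remove the problem, though: if sessions 1 to 3 are averaged, no single CAPS is closest to all of them and the SAP does not say which applies.
- **Remedy.** Switching to simple change is not a clean repair, because change is distorted in the opposite direction when adherence tracks starting severity.

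The visit intervals are also approximate, and the schedule says only that V15 to V17 come before V18, so late integrative sessions are borderline. That does not affect V14 or V29 themselves. What the reply does not answer is the mismatch between a raw score and an aim of reduction, which holds under any reading of *closest* and appears in both documents.

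**Conclusion.** The point holds within limits. In both documents the adherence analysis uses a raw Global CAPS score to study reduction and so is open to confounding by starting severity: a spurious 0.06 to 0.28 under the assumed ranges. That adherence is in fact related to severity is a possibility, not something the documents show. Under the nearest-in-time reading, the SAP also links V14, V29 and most integrative sessions in the month after them to V13 or V28, which predate them, and early Stage 2 visits may link back to V13. Those pairings cannot reflect an effect of the rated session.

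Priority is low. The analysis is exploratory, runs only if data suffice, and would reliably detect only large correlations after correction. The timing result rests on the plain meaning of *closest* and on V14 following V13. The sizes in steps 3 and 4 rest on assumed correlations and equal SDs.

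**What to change.** In SAP 8.9.3.1:
- Link each rated session to the first independent-rater CAPS after it: V2–V12 to V13, V14–V17 to V18, V19–V27 to V28, and V29–V32 to V33.
- Average ratings by session type within each of those intervals, not across them.
- Use a partial correlation between the averaged rating and the CAPS at the end of the interval, adjusting for the CAPS at its start: screening, V13, the pre-Stage 2 score (V13, or the repeat assessment where more than 8 weeks have passed) and V28 respectively. Use this in place of a raw score or simple change.

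In Protocol 12.0, make the matching change to a baseline-adjusted CAPS, including in the sentence on adherence factors.

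The cost is wording only, since every CAPS needed is already scheduled. Averaging within intervals gives more correlations, each on fewer subjects, so the results should be read as descriptive.
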